Investigator: Title: Dermatologist

[contact] [contact]

Test Site: China-Norm U@Test laboratory

Address: [name],

Shanghai, China

Study Objective: To evaluate the effect of a facial essence on skin barrier and skin condition after 2-week of use; And study on the repair efficacy of skin barrier and condition after receiving Fractional Ultrapulse CO₂-laser. The whole study will be divided into two dimensions to evaluate the product: the comparison of the effect before and after and the comparison with the control group.

Experimental Design:

Mono-centric, single-blind, parallel random and home use design.

Test Areas:

Whole face

Subjects:

70 female adult subjects will be enrolled and divided into 2 groups in the study, recruited according to inclusion and non-inclusion criteria listed below, and at least 60 subjects should complete the whole study (at least 30 subjects per group).

Group 1: Facial Serum Group

- Group 2: Non-treatment Group

Age: 20-50 years old

Measurements:

Clinical Assessment(N=60):

Skin qualities of skin dryness, erythema, papules, desquamation, chromatosis, edema, escharosis, elasticity, evenness, brightness, radiance, smoothness, pores on cheek, crow's feet wrinkle, epithelial confluence and overall healthy appearance will be evaluated by dermatologist at T0 (baseline), T14d (after pre-treatment), T15d (Timm post-procedure), T16d (1-day after self-recovery), T18d (3-day after self-recovery), T22d (7-day after self-recovery), T25d (10-day after self-recovery and product treatment start), T32d (7-day after product treatment), T39d (14-day after product treatment) for all groups.

Lactic Acid Stinging Test (N=60)

Sensitive level by Lactic acid test at T0 (baseline), T14d (after pre-treatment), T25d (10-day after self-recovery and product treatment start), T39d (14-day after product treatment) for all groups.

Instrument Assessment(N=60):

- **Corneometer:** skin hydration on both cheeks will be measured at T0 (baseline), T14d (after pre-treatment), T15d (Timm post-procedure), T16d (1-

day after self-recovery), T18d (3-day after self-recovery), T22d (7-day after self-recovery), T25d (10-day after self-recovery and product treatment start), T32d (7-day after product treatment), T39d (14-day after product treatment) for all groups.

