- 13. Must be willing to comply with all study protocol requirements (pay attention to: only use the skin care products provided during the study, not take topical or oral treatment like retinol, hormone, anti-oxidant health-care products which may affect the anti-aging efficacy of test serum).

Exclusion Criteria:

Prospective subjects meeting any of the criteria listed below will be excluded from participation:

- 1. Pregnant or breast-feeding woman or woman planning pregnancy during the study.
- 2. Subject deprived of rights by a court or administrative order.
- 3. Major subject to a guardianship order.
- 4. Subject residing in a health or social care establishment.
- 5. Patient in an emergency setting.
- 6. Subject with a skin disease in the test areas as well as skin allergy (particularly e.g., acne, rosacea, eczema).
- 7. Volunteer presenting a stable or progressive serious disease (per investigator's assessment).
- 8. Immuno-compromised subject.
- 9. Subject has hyperpigmentation skin symptoms.
- 10. Subject with history of allergy to cosmetic or personal care products or ingredients.
- 11. Subject presenting excessive exposure to sunlight or UV radiation (investigator's assessment).
- 12. Subjects regularly practicing aquatic or nautical sports.
- 13. Subjects regularly attending a sauna.
- 14. Subject with physical highly sensitive constitution;

¹Declaration of Helsinki, 64th World Medical Assembly, Fortaleza, Brazil, October 2013

- 15. Subject with cardiovascular or circulatory history.
- 16. Subject with a history of skin cancer or malignant melanoma.
- 17. Subject with history of medical beauty treatment and taking part in anti-aging studies in the last 3 months before study.
- 18. Intake of antihistamines, antibiotics, corticosteroids, non-steroidal anti-inflammatories or immune-suppressants in the last 6 months before study.

4. Study Design

70 female adult subjects will be enrolled and divided into 2 groups in the study, recruited according to inclusion and non-inclusion criteria listed below, and at least 60 subjects should complete the whole study (at least 30 subjects per group).

• Clinical Assessment(N=60):

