8.1. Statistical considerations

All statistical tests will be two-sided and at the 5% level of significance.

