8.3. Efficacy Verification

8.3.1 Comparison between Time-points

A Shapiro-Wilk test will be used to test for normality of the baseline data (T0) and the change from baseline data (Tn-T0) at post-baseline time points at significance level alpha=0.01. When data passes normality (all normality of the distributions is confirmed for the same parameter), a parametric test will be used to test the null hypothesis that the mean change from baseline is zero. When data fails normality (if one or more normality of the distributions for the same parameter is rejected), a non-parametric test will be used.

Pre-treatment efficacy:

- a) T14d (after pre-treatment), T15d (Timm post-procedure) versus T0 (baseline)
- b) T16d (1-day after self-recovery), T18d (3-day after self-recovery), T22d (7-day after self-recovery), T25d (10-day after self-recovery) versus T15d (Timm post-procedure)

Post-treatment efficacy:

a) T32d (7-day after product treatment), T39d (14-day after product treatment) versus T25d (product treatment start)

The following will be calculated and reported for each evaluation parameter at applicable post-statistical baseline time point(s):

For self-assessment questionnaires, only the data of completing subjects will be analyzed. Questionnaire response options will be in the form of a 5-point semi-structured scale, ranging from one (1) to (5), where the score of one (1) will be the most negative/unfavorable rating and the score of five (5) will be the most positive/favorable rating the product can receive (the scale will also include a mid-point label "neither agree nor disagree"). Responses obtained for each question will be tested for normality using a Shapiro-Wilk test at significance level alpha=0.01, and if the data passes normality testing, mean scores will be used. Responses that are not normally distributed will be assessed using the median response. The percentage of ratings from

4 to 5 ("top XX box %") will be reported.

In the report appendices, raw data and open-ended questionnaire responses will be listed by subject. Data frequency and percentage will be presented for questionnaires and tolerability evaluations. Tolerability tables will also be sent to the Sponsor at the indicated interim data time points; SAQ data will be sent at study completion, for all completing subjects. Medians, means and percentage values will be reported to decimal place (0.0) for all questionnaire data.

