8.3.2 Comparison between Treatments

Paired T test for the same sample size or the independent T test for the different sample size will be used to identify the difference efficacy between treatments if the data fit normal distribution.

- Group 1-Facial Serum group
- **Group 2-**Non-treatment control group

Evaluation	Attributes	Comparison
Clinical Assessment	•Skin symptoms scoring post-procedure: - Dryness - Erythema - Papules - Desquamation - Chromatosis - Edema - Escharosis •Skin qualities: - Skin elasticity - Skin evenness - Skin brightness - Skin smoothness - Skin radiance - Appearance of pores on cheek - Crow's feet wrinkle - Epithelial cell confluence - Over healthy appearance	Group 1 versus Group 2
Instrumental Assessment	Skin hydration by Corneometer Transepidermal water loss (TEWL) by Vapometer Skin elasticity by Cutometer Skin pH by Skin-pH-Meter	
Imaging Analysis	Attributes output from VISIA 7 Attributes output from OCT (The thickness of epidermis)	
LA stinging Test	•Skin symptoms scoring: - Stinging - Itching - Burning	
Tolerance Feedback	•Skin symptoms scoring: - Area - Severity - Start time - During time	

9. Further Study Documentation

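### The only between-group method in 8.3.2 is a t-test with no visit or summary named; testing the four recovery visits one by one costs either error control or power, which one pre-specified comparison over the visits avoids if the effect lasts

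*Protocol*

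**What the plan says.** The Study Objective includes "study on the repair efficacy of skin barrier and condition after receiving Fractional Ultrapulse CO₂-laser", and states that the product is judged both before against after and against the control group. Section 4 and its schedule collect clinical grades, hydration, TEWL, elasticity, pH, VISIA and OCT in both groups straight after the laser on T15d and again at T16d, T18d, T22d and T25d.

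Section 8.3.1 sets the within-group comparisons for recovery visit by visit: "T16d (1-day after self-recovery), T18d (3-day after self-recovery), T22d (7-day after self-recovery), T25d (10-day after self-recovery) versus T15d (Timm post-procedure". Section 8.3.2 sets the comparison between groups: "Paired T test for the same sample size or the independent T test for the different sample size will be used", on condition that the data are normal. Its table lists the attributes to be compared but no visit. Section 8.1 adds "All statistical tests will be two-sided and at the 5% level of significance". The last sentence of 8.3.1 lets a more suitable analysis be used and recorded in a file note or the study report, without saying which.

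On size, the protocol says "70 female adult subjects will be enrolled and divided into 2 groups in the study", and "at least 60 subjects should complete the whole study (at least 30 subjects per group". It gives no effect size, SD, between-visit correlation or target power.

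**The concern.** Repair is a course over ten days, measured four times after the T15d reading. A t-test takes one value per woman. Since 8.3.2 names no summary over visits, and the only visit structure in section 8 is the visit-by-visit list in 8.3.1, the likely outcome is four separate group tests per outcome. The course itself is then never compared.

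The number of tests is large. Section 8.3.2 lists 16 clinical attributes; with hydration, TEWL, R2, R5, R7 and pH there are 22 outcomes. Four visits give 22 × 4 = 88 recovery tests before any imaging, against 22 with one comparison per outcome.

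A visit-wise test also drops a woman from any visit she misses and makes no use of her other recovery visits.

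The quoted sentence has a plainer fault as well: it selects a paired test for two parallel groups whenever their sizes are equal. Equal sizes do not create pairs.

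**Working it through.** The plan states no power figure, so there is none to reproduce.

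**Inputs from the protocol.** Two-sided 5% (8.1); 30 per group (section 4); four recovery visits (8.3.1).

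**Assumptions, not in the protocol.** A standardised difference d = 0.5 at each visit, varied from 0.3 to 1.0; equal correlation r between visits of 0.3 to 0.7, extended to 0.9.

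**Step 1: one visit.** Independent t-test, 58 degrees of freedom, noncentrality d × √(n/2) = 0.5 × √15 = 1.94. Power is 47.8%. Read literally, 8.3.2 would use a paired test at 30 against 30. On arbitrary pairs that has 29 degrees of freedom and 46.5% power, so this fault hardly moves the figures.

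**Step 2: mean of the four visits.** Its variance relative to one visit is (1 + 3r)/4, so the effective difference is 0.5/√((1 + 3r)/4).

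| r | variance factor | effective d | power | gain over one visit |
|---|---|---|---|---|
| 0.3 | 0.475 | 0.725 | 78.9% | +31.1 points |
| 0.5 | 0.625 | 0.632 | 67.3% | +19.5 |
| 0.7 | 0.775 | 0.568 | 58.1% | +10.3 |

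**Step 3: all four visits tested** (simulation, 20,000 trials per case, 30 per group, constant d = 0.5 for the power columns).

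| r | false positives, any visit, unadjusted | power, any visit, unadjusted | power, any visit, Bonferroni | power, four-visit mean |
|---|---|---|---|---|
| 0.3 | 17.3% | 84.8% | 62.4% | 79.6% |
| 0.5 | 15.6% | 78.2% | 55.2% | 67.2% |
| 0.7 | 13.3% | 71.4% | 48.1% | 58.2% |

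Unadjusted testing reaches higher power only by giving up the 5% level. With Bonferroni the level is kept, and the mean gains 79.6 − 62.4 = 17, 67.2 − 55.2 = 12 and 58.2 − 48.1 = 10 points.

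**Step 4: other constant effects.** Gain of the mean over one visit, in points (t-test):

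| d | r = 0.3 | r = 0.5 | r = 0.7 | r = 0.9 |
|---|---|---|---|---|
| 0.3 | 17.4 | 9.6 | 4.7 | 1.3 |
| 0.5 | 31.1 | 19.5 | 10.3 | 3.0 |
| 0.8 | 13.2 | 10.9 | 7.2 | 2.5 |
| 1.0 | 3.2 | 3.0 | 2.3 | 1.0 |

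The range is about 1 to 31 points.

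**Step 5: effects that are not constant.** If the effect fades as 0.5, 0.5, 0.25, 0, the average is 1.25/4 = 0.3125. The mean then has 41% / 33% / 27% power at r = 0.3 / 0.5 / 0.7, below the 48% at either of the first two visits and below Bonferroni testing (45.9% / 42.7% / 38.7%). If the effect of 0.5 exists at one visit only, the average is 0.125 and power is about 8% to 11%, against 48% at that visit.

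**The case against.** **This belongs in the analysis plan.** Covariance structures and summaries over visits often do, and 8.3.2 names no visit. An independent t-test on each woman's mean over the four visits would even be compatible with its wording. So visit-by-visit testing is an inference, and should be called one. But the protocol does not defer the method: it fixes a t-test, and leaves open a choice of visit or summary that matters. The clause at the end of 8.3.1 pre-specifies nothing, because the alternative is unnamed and may be recorded as late as the study report.

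**The power loss is not a fact about this trial.** A reader might infer that the plan simply gives up 10 to 31 points of power. The documents do not support that. The range holds only for a sustained 0.5 SD effect and correlations of 0.3 to 0.7, none of which the protocol states, and it compares against one visit tested alone. If all four visits are tested without adjustment, the cost is false positives and not power. The top of the range may not arise at all: if the groups are compared on change from T15d, equal correlation r between all visits gives changes with variance 2(1 − r) and covariance 1 − r, so they correlate at 0.5 whatever r is.

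**A constant effect is doubtful here.** Section 6.2 gives both groups the same saline and EGF, and no serum, from T15d to T24d. Any group difference at the recovery visits is carry-over from pre-treatment, and nothing in the protocol says that it lasts ten days. This stands. It is a real downside of the four-visit mean and the reason to fix the contrast in advance.

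**Conclusion.** The point holds in a conditional form. Section 8.3.2 fixes a method that takes one value per woman for an objective measured at four recovery visits, and does not say which value. On the natural reading, each outcome either carries a 13% to 17% chance of at least one false-positive visit or, with Bonferroni, has 48% to 62% power for a sustained 0.5 SD difference at 30 per group. One comparison of the four-visit mean has 58% to 79% at a controlled 5%.

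These figures rest on equal between-visit correlations of 0.3 to 0.7 and a constant effect. Over the wider range examined, the gain over a single visit runs from about 1 to 31 points and is never negative for a constant effect; for a short-lived effect it turns into a loss. The pairing of independent groups is an error under any assumption, though small in its effect on power.

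**What to change.** Replace the t-test sentence in 8.3.2, including its paired test. For outcomes measured at T16d, T18d, T22d and T25d:

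- Fit one mixed model for repeated measures with group, visit and group-by-visit terms and an unstructured covariance.
- Pre-specify the mean group difference over the four visits as the recovery result for each outcome.
- Report the visit-specific differences from the same model as supportive.
- For the coarse 0 to 5 grades, compare each woman's mean over these visits by a rank test.

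The cost is a paragraph of analysis text and a little more programming, with no added visits, measurements or subjects. The model also uses the remaining recovery visits of a woman who misses one. The price is lower power than a well-chosen single visit if the carry-over effect is short-lived. The supportive visit-specific estimates would show such a pattern but would not rescue the designated result.

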7.2. Conducting the Study

Pre-screening visit at T-7d

- a. Within 24 hours before screening visit, subjects will be asked not to use any cosmetic product on test areas.
- b. On the arrival, the subject will be informed about the nature of the study and the treatment procedure and a signed and dated informed consent form will be obtained. At the same time, one Photo release form will be also signed from each subject.
- c. A subject screening number will be automatically allocated (SC0X) by CRF.
- d. Demographic data collection.
- e. Medical examination, subject's interview on his medical history and concomitant medications.
- f. Subjects wash face with usual cleanser, then pat dry with clean tissue paper at center.
- g. Acclimatization to the room condition for 30 minutes (the conditions with a well-controlled room temperature (21 ± 1 °C) and humidity ($45\%\pm5\%$).
- h. Clinical assessment by will be done by dermatologist for screening.
- i. Verification of subject eligibility: inclusion/non-inclusion criteria and on-site clinical grading by Dermatologist.
- j. The weighted wash-out products and daily log will be delivered to each subject.
- k. Adverse Events/Local Intolerance will be checked and recorded.

Evaluation visit on T0: Baseline

- a. Subjects wash face with usual cleanser, then pat dry with clean tissue paper at center.
- b. Acclimatization to the room condition for 30 minutes (the conditions with a well-controlled room temperature (21 ± 1 °C) and humidity ($45\%\pm5\%$).
- c. Verification of inclusion/non-inclusion criteria for final eligibility.
- d. Clinical Assessment will be done by dermatologist for T0.
- e. VISIA 7 will be done by trained technician for T0.
- f. OCT scan will be done by trained technician for T0.
- g. Corneometer will be done by trained technician for T0.
- h. Vapometer will be done by trained technician for T0.
- i. Cutometer will be done by trained technician for T0.
- j. pH meter will be done by trained technician for T0.

- k. LA sting test will be done by trained technician for T0.
- The wash-out (standard) products will be weighted and returned to subjects; as the same time, the weighted
 investigational products and daily log will be delivered to each subject according to the randomization
 table.
- m. Adverse Events/Local Intolerance will be checked and recorded.

T0 to T14d

a. Subjects should apply the provided wash-out products twice a day at home, in the morning and in the evening.

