8.2. Descriptive analysis

Descriptive statistics will be provided by one treatment group according to criteria nature:

- Quantitative: number of observed values (nobs), mean, standard deviation (SD), standard error (SE), median, 1st and 3rd quartiles (Q1:Q3), minimum and maximum.
- Qualitative: number of observed values (nobs), number (n) and percentage (%) of patients per class The number of subjects by treatment group in the subject set (N) will be also given.

Descriptive statistics will be performed on per protocol population and will be provided for all demographic and baseline characteristics:

- ✓ Age
- ✓ Gender
- ✓ All attributes of Clinical Assessment Score
- ✓ Score of LA Sting Test
- ✓ Value of Instrumental Measurement Value
- ✓ Value of Imaging Analysis (OCT)

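### Section 8.3.2 compares the groups by a t-test with no baseline term although T0 values are already collected; adjusting for T0 would add precision to the continuous outcomes at almost no cost.

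*Protocol*

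**What the plan says.** The design is a randomised comparison of two separate groups ("Mono-centric, single-blind, parallel random and home use design"). Enrolment is 70, and "at least 60 subjects should complete the whole study (at least 30 subjects per group"). Section 8.1 sets the error rate: "All statistical tests will be two-sided and at the 5% level of significance".

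For Group 1 versus Group 2, section 8.3.2 gives the method as "Paired T test for the same sample size or the independent T test for the different sample size", which "will be used to identify the difference efficacy between treatments if the data fit normal distribution". It names no covariate and does not say whether the visit value or the change is tested.

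The T0 visit in section 7.2 lists clinical grading, VISIA, OCT, Corneometer, Vapometer, Cutometer, pH and the lactic acid test for every subject (for example "Clinical Assessment will be done by dermatologist for T0" and "Corneometer will be done by trained technician for T0"). Investigational product is handed out, according to the randomisation table, only after these measurements.

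The T0 values are used in two places. Section 8.2 describes them: the statistics "will be provided for all demographic and baseline characteristics". Section 8.3.1 uses them as the reference for some of the within-group comparisons over time. The same section ends by allowing an unspecified more appropriate analysis, to be recorded in a note to file or the study report.

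**The concern.** With about 30 completers per group, subjects will differ in hydration, barrier function, elasticity and skin quality before the serum is used. A t-test on visit values leaves all of that variation in the error term, and a chance imbalance at T0 passes directly into the estimated group difference. A t-test on changes subtracts the whole T0 value, which over-corrects when the correlation with T0 is low. Analysis of covariance estimates how much of T0 to remove, and its large-sample variance is never higher than that of either t-test.

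The within-group tests in 8.3.1 do not fill the gap, since testing each group's change against zero does not adjust the contrast between groups. What is at stake is the chance of detecting a real group difference in a small trial, and the width of its confidence interval.

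**Working it through.** **Is there a figure to reproduce?** No. The protocol states no power, effect size, standard deviation or derivation of the sample size.

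**Inputs from the protocol.** n = 30 completers per group (Study Design); two-sided 5% (8.1); t-test without covariate (8.3.2); T0 measured in both groups (7.2).

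**Assumed inputs.** Standardised difference d (group difference divided by the between-subject SD of the visit value) and correlation rho between T0 and the visit value, with equal SDs at the two times. Both are varied below.

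**Formulas.** Relative to the visit-value variance, the error variance is multiplied by:

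- t-test on visit values: 1, with 58 degrees of freedom
- t-test on changes: 2(1 − rho), with 58 degrees of freedom
- analysis of covariance on T0: 1 − rho², with 57 degrees of freedom

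Power comes from the noncentral t distribution with noncentrality d × √(n/2) / √(factor).

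**Example, d = 0.5 and rho = 0.5.** √(30/2) = 3.873.

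- t-test: noncentrality 0.5 × 3.873 = 1.936, power 47.8%. On changes the factor is 2(1 − 0.5) = 1, so power is the same.
- Covariance analysis: factor 1 − 0.25 = 0.75, √0.75 = 0.866, noncentrality 1.936 / 0.866 = 2.236, power 59.4%. The gain is 11.6 points.

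A simulation of 20,000 trials gave 47.6% and 58.9%. Equal precision without adjustment would need 30 / 0.75 = 40 per group. The difference detectable with 80% power falls from 0.736 SD to 0.736 × 0.866 = 0.637 SD.

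**Varying d at rho = 0.5** (gains taken before rounding; identical for visit values and changes):

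| d | t-test | T0-adjusted | gain (points) |
|---|---|---|---|
| 0.2 | 11.9% | 14.2% | 2.4 |
| 0.3 | 20.8% | 26.1% | 5.3 |
| 0.4 | 33.2% | 42.0% | 8.9 |
| 0.5 | 47.8% | 59.4% | 11.6 |
| 0.6 | 62.8% | 75.1% | 12.4 |
| 0.7 | 76.0% | 86.8% | 10.8 |
| 0.75 | 81.5% | 90.9% | 9.4 |
| 0.8 | 86.1% | 94.0% | 7.9 |
| 0.9 | 92.9% | 97.7% | 4.8 |

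**Varying rho at d = 0.5:**

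| rho | visit values | changes | T0-adjusted | gain over values | gain over changes |
|---|---|---|---|---|---|
| 0.3 | 47.8% | 36.3% | 51.4% | 3.6 | 15.1 |
| 0.5 | 47.8% | 47.8% | 59.4% | 11.6 | 11.6 |
| 0.7 | 47.8% | 69.1% | 76.0% | 28.2 | 6.9 |

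Even if the better of the two t-tests were always chosen, the variance ratio is 0.91/1 = 0.91 at rho = 0.3, 0.75/1 = 0.75 at rho = 0.5 and 0.51/0.6 = 0.85 at rho = 0.7. Adjustment still gains 3.6, 11.6 and 6.9 points at d = 0.5. At rho = 0 there is no gain over visit values.

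**The test as written at exactly 30 v 30.** The rule in 8.3.2 then selects a paired test. With arbitrary pairing of unrelated subjects it has 29 degrees of freedom and 46.5% power at d = 0.5, about one point below the 58-df test used above.

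**The case against.** The strongest reply is that an unadjusted t-test between randomised groups is valid, that no stated power is missed, and that model details usually belong to a statistical analysis plan, which is not shown. The first two parts stand: a reader might infer that the planned comparison is biased, or that the trial fails its own power target, and the protocol supports neither. The third part carries less weight. Section 8.3.2 is not silent; it names a method, and that method is the less efficient one. The clause in 8.3.1 allowing another analysis names no model and lets the choice be recorded as late as the study report, so it does not supply the adjustment.

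A second reply is that the size of the gain rests on assumptions. This also stands, and limits the point in three ways.

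- A reader might carry the 9 to 12 points over to every outcome. The calculation is for continuous outcomes. The clinical grades and lactic acid scores are ordinal, and no gain has been computed for them.
- One correlation cannot be expected to hold at all visits. The laser procedure falls between T14d and the recovery visits, and T0 may predict post-laser values poorly; the gain is then smaller.
- Signs such as edema, escharosis, papules and desquamation may hardly vary at T0, in which case adjustment gains little or nothing.

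Nor is T0 the only baseline variable available: age is collected too. T0 is preferred because it is the same measurement on the same subject, not because nothing else exists.

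**Conclusion.** The point holds as a nearly free improvement. The planned group comparison gives up precision that the T0 measurements could supply, without being biased or invalid.

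For hydration, TEWL, R2/R5/R7, pH, OCT and VISIA outcomes, the loss is about 9 to 12 points of power at 30 per group if rho is 0.5 and d lies between 0.4 and 0.75. Both are assumptions. Outside those values the size changes widely, as the tables show, so the range should accompany any headline figure. The direction is more secure than the size: over rho of 0.3 to 0.7, T0 adjustment beats both readings of 8.3.2, which also makes it unnecessary to choose between values and changes.

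The rule that picks a paired test when group sizes are equal is a separate error in the same sentence. Correcting it alone would leave an unadjusted independent t-test, so this point would remain.

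**What to change.** Reword section 8.3.2 as follows.

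- **Continuous outcomes:** estimate the Group 1 versus Group 2 difference at each visit by analysis of covariance for independent groups, with the visit value as outcome and group and the subject's own T0 value as terms. Report the adjusted difference with its 95% confidence interval.
- **T32d and T39d:** use T0 as covariate, not T25d. T25d is measured after allocation and after two weeks of serum in Group 1, so adjusting for it could remove part of the treatment effect. State that the T0-adjusted difference at these visits is the combined effect of pre- and post-treatment; it does not answer the T25d-referenced question in 8.3.1.
- **Ordinal grades and lactic acid scores:** use a rank-based analysis of covariance with the same T0 term, without claiming a power gain.
- **Signs with little or no variation at T0** (such as edema, escharosis, papules, desquamation): no baseline term is needed. Name these signs before the data are seen.

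The cost is a paragraph of wording and one degree of freedom per model for the continuous outcomes. No measurement, visit or subject is added.

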5.1. Clinical Assessment (N=60)

Skin qualities will be evaluated by validated Dermatologist at T0 (baseline), T14d (after pre-treatment), T15d (Timm post-procedure), T16d (1-day after self-recovery), T18d (3-day after self-recovery), T22d (7-day after self-recovery), T25d (10-day after self-recovery and product treatment start), T32d (7-day after product treatment), T39d (14-day after product treatment). Every effort will be made to have the Dermatologist grade the same subjects throughout the study. The Dermatologist will not be allowed to reference previous scores at post-baseline assessments. The half-point scores (0.5) increment may be used when necessary to describe the skin appearance more accurately in Griffith 10-points scale. The tendentious half-point scores (0.4 or 0.6) may be used in scales from Asian skin aging atlas.

- **Skin symptoms post-procedure** include dryness, erythema, papules, desquamation, chromatosis, edema, escharosis will be evaluated.
- **Skin qualities** include the elasticity, skin evenness, skin brightness, skin smoothness, skin radiance, pores on cheeks and over healthy appearance will be evaluated.

Attributes in 6-points scale (0 to 5 scale):

- Dryness (0 to 5, 0 score means no any symptom, 5 score means very serious)
- Erythema (0 to 5, 0 score means no any symptom, 5 score means very serious)
- Papules (0 to 5, 0 score means no any symptom, 5 score means very serious)
- Desquamation (0 to 5, 0 score means no any symptom, 5 score means very serious)
- Chromatosis (0 to 5, 0 score means no any symptom, 5 score means very serious)
- Edema (0 to 5, 0 score means no any symptom, 5 score means very serious)
- Escharosis (0 to 5, 0 score means no any symptom, 5 score means very serious)
- Epithelial cell confluence (0 to 5 scale)

0=none

1=very slight (up to 10%)

2=slight (11%-30%)

3=moderate (31%-60%)

4=extensive (61%-90%)

5=almost complete or complete (91%-100%)

Attributes in Atlas:

- Crow's feet wrinkles (0 to 6 scale)

The parameter will be scored according to the Skin Aging Atlas of 0 to 6 on Page 40 to 41.

Attributes in Griffith 10-points scale (0 to 9 scale):

Parameter	Type of Grading	None (Best possible condition) (=0)	Mild (1-3)	Moderate (4-6)	Severe (Worst possible condition) (7-9)

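### Section 8.3.1 tests normality of differences that six of its eight contrasts do not use, and section 8.3.2 names a between-group test only for normal data although most listed outcomes are ordinal or categorical

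*Protocol*

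**What the plan says.** Section 8.3.1 (comparison between time-points) applies Shapiro-Wilk to the T0 values and to the "change from baseline data (Tn-T0) at post-baseline time points at significance level alpha=0.01". If every distribution passes, a parametric test of mean change is used; "if one or more normality of the distributions for the same parameter is rejected", a non-parametric one. The contrasts it then lists are T14d and T15d against T0; T16d, T18d, T22d and T25d against T15d; and T32d and T39d against T25d. A closing sentence allows an unnamed alternative analysis, to be recorded in a file note or the study report.

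Section 8.3.2 (comparison between treatments) offers a paired or an independent t-test to "identify the difference efficacy between treatments if the data fit normal distribution". It names no other test and does not say how normality is judged. Its table sends to this comparison the 16 clinical attributes, the instrument and imaging outputs, three lactic acid symptoms and four diary items: "Area - Severity - Start time - During time".

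Section 5.1 defines the clinical scales. Seven symptoms are graded in the manner of "Escharosis (0 to 5, 0 score means no any symptom, 5 score means very serious"; epithelial confluence is also 0-5, crow's feet 0-6, and seven skin qualities 0-9 with half points. Section 5.2 scores lactic acid symptoms 0-3. Annex 11.4 codes diary area by facial site and start time in four classes.

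**The concern.** A normality check can only inform a paired comparison if it looks at the difference being tested. Here it looks at T0, which has no bearing on a paired test, and at changes from T0, which are the tested difference for two contrasts only. The recovery and post-treatment contrasts carry most of the study objective and go unchecked. Because one rejection moves a whole parameter, similar outcomes can also receive different tests by chance.

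Between groups, the stated rule covers one case only. If most outcomes fall in the other case, the test for much of the randomised comparison is chosen once data are in hand. Listing a site code in that table adds an item for which a difference in means has no meaning.

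**Working it through.** **Inputs from the protocol.** Comparisons two-sided at 5% (8.1); normality check at 0.01 (8.3.1); "at least 60 subjects should complete the whole study (at least 30 subjects per group" (synopsis and section 4); nine assessments from T0 to T39d, four for lactic acid. No means, SDs or correlations are given, so those below are assumptions.

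**Step 1. Checked against tested differences.**

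| Contrasts in 8.3.1 | Number | Difference tested | Checked? |
|---|---|---|---|
| T14d, T15d against T0 | 2 | Tn-T0 | yes |
| T16d, T18d, T22d, T25d against T15d | 4 | Tn-T15d | no |
| T32d, T39d against T25d | 2 | Tn-T25d | no |

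So 4 + 2 = 6 of 8 are not checked.

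**Step 2. Whether this can matter.** Two simulated settings at n=30 with a skewed step between visits:
- Log-normal change from T25d to T32d: T32d-T0 rejected 3.5% of the time, T32d-T25d rejected 82%.
- Log-normal change from T15d to T22d: T22d-T0 rejected 50%, T22d-T15d rejected 89%.

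The check can pass data whose tested difference is clearly skewed. How often depends on the assumed spread at the other visits.

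**Step 3. Switching by chance.** A parameter seen at nine visits has nine checks (T0 plus eight changes). For normal data and independent checks:

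1 - (1 - 0.01)^9 = 1 - 0.9135 = 0.0865, or 8.6%.

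The changes share T0 and so are not independent; a simulation with shared T0 and correlation 0.5 gave 8.9%. With four checks, as for lactic acid, 1 - 0.99^4 = 3.9%.

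**Step 4. Kind of outcome in the 8.3.2 table.** Counting the Cutometer as R2, R5 and R7 and leaving out VISIA, whose outputs are not named: 16 clinical + 6 instrument + 1 OCT + 3 lactic acid + 4 diary = 30. Ordinal or categorical: 16 + 3 + 3 (area, severity, start time) = 22. Of these, 14 are coarse (eight 0-5 scores, three lactic acid, three diary) and 8 are finer (seven 0-9 half-point scores and crow's feet).

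**Step 5. How often these fail Shapiro-Wilk at 0.01, n=30.** Rounded-normal scores, assumed parameters:

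| Scale | One distribution | Whole-parameter rule |
|---|---|---|
| 0-5, whole numbers | 66% (mean 2.5, SD 1) to 100% (near floor) | 99.9-100% |
| 0-3, single score | 100% | 100% |
| 0-9, half points | 2% (SD 1.5), 4% (SD 1), 31% (SD 0.6) | 17% (SD 1.5, corr. 0.5), 32% (SD 1, corr. 0.5), 86% (SD 1, corr. 0.8) |
| Continuous normal | 1% | 8.9% |

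Whole numbers for the 0-5 scores are an assumption: section 5.1 mentions half points only for the 0-9 scale. The 0-3 row treats lactic acid as one score. Section 5.2 uses the lactic-minus-water difference after ratings at three times, which has more levels and may fail less often.

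**Step 6. Whether a t-test would be wrong on such scores.** Independent t-test at 30 per group, two-sided 5%, no true difference: type I error 5.2% (0-5 near floor), 5.1% (0-5 centred), 4.9% (0-3).

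**The case against.** The strongest reply has four parts.

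- **A t-test would be acceptable anyway.** Step 6 supports this. A reader might infer that the ordinal outcomes have no valid test; the evidence does not bear that out. What stands is narrower: the protocol makes its t-test conditional on normality and names nothing for the other case.
- **An SAP may supply the missing branch.** It may. But the conditional rule and the use of Tn-T0 are stated in the protocol itself. The non-parametric clause in 8.3.1 concerns change over time, and the open clause that follows is settled afterwards, so neither fills the gap.
- **Within groups the gate mostly lands well.** True for the 0-5 scores, which it would nearly always send to a non-parametric test. It does not help the half-point scores and instruments, where the choice is uncertain.
- **Reporting already covers part of this.** Section 8.3.1 promises medians, means and top-box percentages for questionnaires, and frequencies and percentages for tolerability. Questionnaire reporting needs no change. A reader might also infer that site codes will be averaged; no sentence says so. What remains is that area and start time sit in a comparison table for which only t-tests are named.

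Two further inferences go too far. Shapiro-Wilk is named only in 8.3.1, so it cannot be said to govern 8.3.2, which leaves its own normality condition undefined. Nor can it be said that all clinical scores will fail: the 0-9 half-point scores may pass.

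**Conclusion.** The point holds in a limited form and should be corrected. Two parts rest on the text alone: six of eight within-group contrasts are not the differences checked for normality, and the only between-group rule covers normal data while about 22 of 30 named attributes are ordinal or categorical. That whole-number 0-5 scores would almost surely fail a Shapiro-Wilk check applied as in 8.3.1, and that 0-9 half-point scores may or may not, depends on the assumed distributions. The 8.6% switching rate assumes nine independent checks.

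The consequence is that the test for many outcomes is chosen after data are seen, and can differ between similar outcomes by chance. It is not that a t-test would give wrong error rates, which the simulations contradict. Choosing a paired test because the groups are of equal size, in the same sentence of 8.3.2, is a separate problem and not part of this point.

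**What to change.** Amend protocol section 8.3 before group-level data are seen. Drop the normality gate and fix each test by scale:

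- **Ordinal grades and lactic acid scores.** Between groups, Wilcoxon rank-sum on the change from the relevant reference visit, or on the score itself where the reference is constant. Within groups, signed-rank on the contrast actually listed.
- **Instruments and OCT.** Between groups, ANCOVA with the T0 value as covariate. Decide in advance whether TEWL is log-transformed; deciding from the residuals would be another data-driven switch. Within groups, keep the parametric test of mean change, applied to the listed contrast.
- **Diary.** Compare the proportion of women with any reaction (Fisher exact) and the worst severity (rank-sum). Tabulate area and start time only.
- **Questionnaires.** No change.

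Cost: a signed amendment under section 9.1, and slightly less power than a t-test where scores are close to normal. Data collection does not change.
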